11.2. Standard data derivation

11.2.1. Date derivation

- SAS date derived from a character date: in case day is missing, 15 is used. In case day & month are missing, 30June is used.
- Onset day for an event (ae, medication, vaccination, ...): the onset day is the number of days between the last study vaccination & the onset/start date of the event. This is 1 for an event starting on the same day as a vaccination. See SAS date derived in case the start date of the event is incomplete.
- Duration: Duration of an event is expressed in days. It is the number of days between the start & the stop dates + 1. Therefore duration is 1 day for an event starting & ending on the same day.

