8.3. Detecting and recording adverse events and serious adverse events

8.3.1. Time period for detecting and recording adverse events and serious adverse events

All AEs starting within 31 days following administration of Dose 1 and Dose 2 of the HRV vaccine (Day 1 to Day 31) must be recorded into the appropriate section of the eCRF, irrespective of intensity or whether or not they are considered vaccination-related.

The time period for collecting and recording SAEs will begin at the receipt of study vaccines until the subject is discharged from the study. See Section [8.4](#) for instructions on reporting of SAEs.

All AEs/SAEs leading to withdrawal from the study will be collected and recorded from the time of the receipt of study vaccines.

In addition to the above-mentioned reporting requirements and in order to fulfil international reporting obligations, SAEs that are related to study participation (i.e., protocol-mandated procedures, invasive tests, a change from existing therapy) or are related to a concurrent GSK medication/vaccine will be collected and recorded from the time the subject consents to participate in the study until she/he is discharged from the study.

An overview of the protocol-required reporting periods for AEs and SAEs is given in [Table 12](#).

Table 12 Reporting periods for collecting safety information

Event	Pre-V1*	Visit 1	7 d	30 d	Visit 2	7 d	30 d	Visit 3	7 d	30 d	Visit 4	ESFU contact
			post-V1	post-V1		post-V2	post-V2		post-V3	post-V3		
		Day 1			Month 2			Month 4			Month 5	Month 10
Solicited general AEs			■	■		■	■					
Unsolicited AEs			■	■	■	■	■					
AEs/SAEs leading to withdrawal from the study			■	■	■	■	■	■	■	■		
SAEs			■	■	■	■	■	■	■	■		
SAEs related to study participation or concurrent GSK medication/vaccine			■	■	■	■	■	■	■	■		

* i.e., consent obtained. V: vaccination; Post-V: post-vaccination.

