5.1.2. Per-protocol Set for analysis of immunogenicity (PPS)

The PPS for immunogenicity will include all eligible subjects from the ES:

- who have received the study vaccines according to their random assignment,
- who comply with the vaccination schedule of routine infant vaccines and HRV vaccines as per [Table 5](#),
- for whom the routine infant vaccines were administered according to the protocol as per [Table 4](#),
- for whom the HRV vaccine liquid or lyophilized formulation was administered according to protocol,
- who have not received a vaccine not specified or forbidden in the protocol up to Visit 4 blood sampling,
- who had not received medication forbidden by the protocol up to Visit 4 blood sampling,
- whose underlying medical condition(s) was (were) not forbidden by the protocol up to Visit 4 blood sample,

- for whom data concerning immunogenicity endpoint measures are available. This will include subjects for whom assay results are available for antibodies against at least one routine infant vaccine antigen component,
- who comply with the blood sampling schedule after the 3rd dose of Pediarix, Hiberix and Prevenar 13 as per [Table 5](#),
- who have no concomitant infection up to Visit 4 blood sample, which may influence the immune system.

Table 4 Dosage and administration

Type of contact and time-point	Study group	Treatment name	Volume to be administered	Route ¹	Site		
					Location	Directionality ²	Laterality
Visit 1, Visit 2	HRV Liq	HRV Liquid	1.5 ml	O	Not applicable	Not applicable	Not applicable
Visit 1, Visit 2	HRV Lyo	HRV Lyophilized	1 ml	O	Not applicable	Not applicable	Not applicable
Visit 1, Visit 2, Visit 3	HRV Liq, HRV Lyo	Pediarix	0.5 ml	IM	Thigh	Upper	Right
Visit 1, Visit 2, Visit 3	HRV Liq, HRV Lyo	Hiberix	0.5 ml	IM	Thigh	Anterolateral	Right
Visit 1, Visit 2, Visit 3	HRV Liq, HRV Lyo	Prevenar 13	0.5 ml	IM	Thigh	Lower	Left

¹Oral (O), Intramuscular (IM)² Directionality is a qualifier for further detailing the location of the vaccine administration.**Table 5 Maximum allowed interval between visits**

Interval	Allowed length of interval
Visit 1→Visit 2	49 days-83 days after Dose 1 of study vaccines 1
Visit 2→Visit 3	56 days-83 days after Dose 2 of study vaccines 1
Visit 3→Visit 4	21 days-48 days after Dose 3 of study vaccines 1
Visit 3→ESFU	180 days-210 days after Dose 3 of study vaccines

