6.4. Analysis of safety

6.4.1. Analysis of safety planned in the protocol

The ES will be used for the analysis of safety.

The following calculations will be performed for each group:

The percentage of doses and of subjects reporting at least one symptom (solicited or unsolicited) during the 8 day (Day 1-Day 8) solicited follow-up period post-vaccination will be computed, along with exact 95% CI. The same calculations will be done for symptoms (solicited or unsolicited) rated as grade 3 in intensity, those assessed as causally related to vaccination, those rated as grade 3 in intensity with causal relationship to vaccination and those that resulted in a medically attended visit.

The percentage of doses and of subjects reporting each individual solicited general symptom will be computed, over the 8 day (Day 1-Day 8) solicited follow-up period post-vaccination, along with exact 95% CI. The same calculations will be done for each individual general solicited symptom rated as grade 3 in intensity, those assessed as causally related to vaccination, those rated as grade 3 in intensity with causal relationship to vaccination and those that resulted in a medically attended visit. For fever, additional analyses will be performed by 0.5°C increments. These calculations will also be performed by sex and race.

The verbatim reports of unsolicited AEs will be reviewed by a physician and the signs and symptoms will be coded according to MedDRA. Every verbatim term will be matched with the appropriate Preferred Term. The percentage of subjects with unsolicited AEs occurring within 31 day (Day 1-Day 31) follow-up period after any dose with its exact 95% CI will be tabulated by group, and by preferred term. Similar tabulation will be done for unsolicited AEs rated as grade 3, for unsolicited AEs with causal relationship to vaccination, for unsolicited AEs rated as grade 3 with causal relationship to vaccination and those that resulted in a medically attended visit.

The percentage of subjects who started taking at least one concomitant medication, antipyretic medication and prophylactic antipyretic medication during the 8 day (Days 1-8) and 31 day (Days 1-31) follow-up period post-vaccination will be tabulated by dose, overall per subject and over all the doses.

Subjects who experienced at least one SAE during the entire study period (from Dose 1 till ESFU Contact at Month 10) will be reported and the SAEs will be described in detail.

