11.2.2. Dose number

- The study dose number is defined in reference to the number of study visits at which vaccination occurred. More specifically dose 1 refers to all vaccines administered at the first vaccination visit while dose 2 corresponds to all vaccinations administered at the second vaccination visit even if this is the first time a product is administered to the subject.
- Relative dose: the relative dose for an event (AE, medication, vaccination) is the most recent study dose given before an event. In case the event takes place on the day a study dose is given, the related dose will be that of the study dose, even if the event actually took place before vaccination. For instance, if an adverse event begins on the day of the study vaccination but prior to administration of the vaccine, it will be assigned to this dose. In case a study dose is not administered and an event occurs after the subsequent study dose (eg 3rd study dose), the relative dose of the event will be study dose associated to the subsequent study dose (eg dose 3).
- The number of doses for a product is the number of time the product was administered to a subject.
- The incidence per dose is the number of vaccination visits at which an event was reported among all vaccination visits.

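### Incomplete adverse event and medication start dates are imputed without reference to the vaccination date, so some can be placed before the dose, under the wrong dose, or past Day 31

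*SAP*

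**What the plan says.** SAP 11.2.1 gives one rule for incomplete dates: "in case day is missing, 15 is used. In case day & month are missing, 30June is used". It applies to event onset by cross-reference: "See SAS date derived in case the start date of the event is incomplete". In the same section, "the onset day is the number of days between the last study vaccination & the onset/start date of the event", counted as 1 on the vaccination day. Under SAP 11.2.2, "the relative dose for an event (AE, medication, vaccination) is the most recent study dose given before an event". An event on a vaccination day goes to that day's dose, even if it began before the injection.

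These derived values feed the safety tables. SAP 6.4.1 tabulates "The percentage of subjects with unsolicited AEs occurring within 31 day (Day 1-Day 31) follow-up period after any dose". It also tabulates any symptom (solicited or unsolicited) over Days 1-8, and concomitant medication over Days 1-8 and Days 1-31. Serious adverse events have a wider scope: "Subjects who experienced at least one SAE during the entire study period (from Dose 1 till ESFU Contact at Month 10) will be reported".

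SAP 11.2.6, on missing data, adds nothing on partial dates. No section says what happens to an event whose imputed onset falls before Dose 1.

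**The concern.** The investigator may know that an event followed vaccination and yet record only the month. The rule then replaces that knowledge with a fixed calendar date, which can contradict it. A true in-window event can leave the 31-day table, or be counted under an earlier dose with a long onset time. SAP 11.2.5 counts subjects with no reported event as event-free and keeps them in the denominator, so a subject whose only event is misplaced lowers the tabulated percentage.

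The rule also runs against the SAP's own same-day convention, which settles uncertain timing by counting the event as post-dose. The fixed-date rule can do the reverse.

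**Working it through.** The plan states no figure to reproduce, so the check applies the rule itself by exact enumeration.

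**Inputs**
- Imputation rule and onset-day definition: SAP 11.2.1. Onset day = event date - dose date + 1.
- Windows of Days 1-31 and Days 1-8, and the serious-event period of Dose 1 to Month 10: SAP 6.4.1.
- Dose 1 to Dose 2 interval: SAP Table 5 allows "49 days-83 days after Dose 1 of study vaccines"; Protocol Table 5 gives 60 days as optimal.
- Assumptions: dose dates uniform over 365 calendar days, and true onset uniform over the window.
- Share of events with a missing day: not in the documents; a range of 0.5% to 5% is assumed.

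**Worked examples**
- Dose on 20 March, true onset 24 March (Day 5), recorded as March. Imputed 15 March: 15 - 20 + 1 = -4, before the dose.
- Dose on 5 March, true onset 2 April (Day 29), recorded as April. Imputed 15 April: Day 42, outside the window.
- Dose 1 on 21 March, Dose 2 on 20 May (60 days later), true onset 24 May, recorded as May. Imputed 15 May: attributed to Dose 1 at Day 56, so outside both 31-day windows.

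**Day missing, true onset on Days 1-31** (365 x 31 = 11,315 cases)
- Before the dose: 1,523 / 11,315 = 13.5%.
- After Day 31: 1,260 / 11,315 = 11.1%.
- Leaving the window: 2,783 / 11,315 = 24.6%; staying: 75.4%.

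With dose intervals of 49, 60 or 83 days, no Dose 2 event imputed before Dose 2 lands in the Dose 1 window. These events leave the any-dose table altogether.

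**Day missing, true onset on Days 1-8** (365 x 8 = 2,920 cases; relevant to the 8-day medication and any-symptom tables)
- Before the dose: 1,144 / 2,920 = 39.2%.
- After Day 8: 1,008 / 2,920 = 34.5%.
- Leaving the 8-day window: 73.7%.

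**Day and month missing, true onset on Days 1-31**
- Before the dose 46.3%, after Day 31 45.2%; together 91.5%.

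**Movement the other way.** Of day-missing events truly after Day 31 and before Dose 2, 42.4%, 26.3% and 14.7% move into a window at intervals of 49, 60 and 83 days.

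**Serious adverse events.** With onset uniform over 301 days from Dose 1, 1.4% (day missing) or 15.5% (day and month missing) are imputed before Dose 1.

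**Absolute scale.** 0.005 x 0.246 = 0.1% and 0.05 x 0.246 = 1.2% of all in-window unsolicited events.

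**With the fix.** Setting the onset to the later of the dose date and the first day of the recorded month (or year) loses 0 of 11,315 true in-window events.

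**The case against.** The strongest reply is that very little data is touched. Unsolicited events come from diary cards that are verified with the parents, and unreturned cards are chased (Protocol 5.6.13). Omissions in the eCRF may be queried (Protocol 11.1). A missing month for an event on such a card is unlikely, so the 91.5% describes a rare case. Even with the day missing, about three quarters of events stay in the window. Both groups get the same rule, and SAP section 7 makes all safety analyses descriptive. All of this stands, and it limits the size of the problem. It does not make the derivation correct, and neither document commits to resolving every partial date.

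A second reply is that the errors run both ways. Some movement inward exists, as shown above. But Protocol 8.3.1 requires non-serious events in the eCRF only for "All AEs starting within 31 days following administration of Dose 1 and Dose 2 of the HRV vaccine", so few later events should be there to move in. The expected net effect on the unsolicited table is loss.

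A reader might go further and infer that serious adverse events drop out of the safety report, or that an early intussusception could vanish, since Protocol 6.6 places that risk mostly within 7 days of the first dose. The documents do not support this. Serious events are reported from Dose 1 to Month 10 and described in detail, whatever the 31-day window. Only an onset imputed before Dose 1 raises a question, and the SAP does not say that such events are removed. Nor do solicited symptoms depend on this rule: SAP 11.2.5 takes them from documented presence or absence and daily recordings.

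**Conclusion.** The point holds in a limited form. The rule applies to event onset, ignores the vaccination date, and can misplace unsolicited adverse events and concomitant medications with incomplete start dates. On uniform dose and onset dates, 24.6% of day-missing true Day 1-31 events leave the 31-day window, and 91.5% if the month is also missing. The effect on the whole table is probably small: about 0.1% to 1.2% of in-window unsolicited events, on the assumed 0.5% to 5% with a missing day. For serious adverse events the gap is that handling of an onset imputed before Dose 1 is not stated; loss of such events is not shown. No confirmatory conclusion is affected. The change is worth making because it is cheap and removes a known error from the safety tables.

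**What to change.** Replace the rule for the start dates of adverse events, serious adverse events and medications:

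- Use the earliest date compatible with the recorded partial date that is on or after the relevant study dose. This includes the case where the recorded month follows the dose month: dose on 5 March and event in April gives 1 April (Day 28), not 15 April (Day 42). Keeping the 15th whenever no dose falls in the recorded month would leave the 11.1% late loss in place.
- Cap the imputed date at the event's end date or the date it was reported, whichever is earlier.
- Define the relevant dose as the most recent compatible dose given before the visit at which the event was reported. A dose given at that same visit does not count; otherwise an event reported at Visit 2 could become Day 1 of Dose 2.
- Keep the 15th and 30 June only where the partial date is not compatible with onset after any study dose, and for dates other than event starts.
- State that serious adverse events recorded as post-vaccination stay in the serious-event report whatever the imputed date.
- Flag imputed onsets in the listings.

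The cost is one SAP paragraph and a small programming change before database lock. The downside is that some events will be placed too early or counted as post-dose when they were not, and some day-missing events truly after Day 31 will be drawn into the window. For safety reporting this is the conservative direction.

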11.2.2. Dose number

- The study dose number is defined in reference to the number of study visits at which vaccination occurred. More specifically dose 1 refers to all vaccines administered at the first vaccination visit while dose 2 corresponds to all vaccinations administered at the second vaccination visit even if this is the first time a product is administered to the subject.
- Relative dose: the relative dose for an event (AE, medication, vaccination) is the most recent study dose given before an event. In case the event takes place on the day a study dose is given, the related dose will be that of the study dose, even if the event actually took place before vaccination. For instance, if an adverse event begins on the day of the study vaccination but prior to administration of the vaccine, it will be assigned to this dose. In case a study dose is not administered and an event occurs after the subsequent study dose (eg 3rd study dose), the relative dose of the event will be study dose associated to the subsequent study dose (eg dose 3).
- The number of doses for a product is the number of time the product was administered to a subject.
- The incidence per dose is the number of vaccination visits at which an event was reported among all vaccination visits.

11.2.3. Demography

- Age: Age at the reference activity, computed as the number of complete weeks between the date of birth and the reference activity.
- Conversion of weight to kg: the following conversion rule is used:
 - Weight in Kilogram= weight in Pounds / 2.2
 - Weight in Kilogram =weight in ounces / 35.2
 - The result is rounded to 2 decimals.
- Conversion of height to cm: the following conversion rule is used:
 - Height in Centimetres = Height in Feet * 30.48
 - Height in Centimetres = Height in Inch * 2.54
 - The result is rounded to the unit (ie no decimal).
- Conversion of temperature to °C: the following conversion rule is used:
 - Temperature in Celsius = ((Temperature in °Fahrenheit -32) *5)/9
 - The result is rounded to 1 decimal.

11.2.4. Immunogenicity

- For a given subject and given immunogenicity measurement, missing or non-evaluable measurements will not be replaced.

The Geometric Mean Concentrations (GMCs) calculations are performed by taking the anti-log of the mean of the log titre transformations. Antibody concentrations below the cut-off of the assay will be given an arbitrary value of half the cut-off of the assay for the purpose of GMC calculation.

Note that in the case of HBsAg the values between the assay cut-off of 6.2 mIU/mL (=lower level of detection) and 7.65 mIU/mL (=lower level of quantification) will be assigned the arbitrary value of 6.2 for the GMC computation. The assay cut-off value is defined by the laboratory before the analysis and is described in Section 5.7.3 of the protocol, except for rotavirus IgA, whose lower level of quantification is defined to be 13 U/mL.

- For all assays but rotavirus IgA, a seronegative subject is a subject whose antibody concentration is below the cut-off value of the assay. A seropositive subject is a subject whose antibody concentration is greater than or equal to the cut-off value of the assay. For the rotavirus IgA seropositivity is defined as having a concentration above 20 U/mL.
- In general, the assay cut-off is the value under which there is no quantifiable result available. For an assay with a specific ‘assay cut_off’, numerical immuno result is derived from a character field (rawres):
 - If rawres is ‘NEG’ or ‘-’ or ‘(-)’, numeric result= assay cut_off/2,
 - if rawres is ‘POS’ or ‘+’ or ‘(+)’, numeric result = assay cut_off,
 - if rawres is ‘< value’ and value<=assay cut_off, numeric result =assay cut_off/2,
 - if rawres is ‘< value’ and value>assay cut_off, numeric result =value,
 - if rawres is ‘> value’ and value<assay cut_off, numeric result =assay cut_off/2,
 - if rawres is ‘> value’ and value>=assay cut_off, numeric result =value,
 - if rawres is ‘<= value’ or ‘>= value’ and value<assay cut_off, numeric result =assay cut_off/2,
 - if rawres is ‘<= value’ or ‘>= value’ and value>=assay cut_off, numeric result =value,
 - if rawres is a value < assay cut_off, numeric result = assay cut_off/2,
 - if rawres is a value >= assay cut_off, numeric result = rawres,
 - else numeric result is left blank.

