¹ GSK Biologicals laboratory refers to the Clinical Laboratories Sciences (CLS) in Rixensart, Belgium; Wavre, Belgium or a validated laboratory designated by GSK Biologicals.

SER = Serum

S pneu = Streptococcus pneumoniae

IgA = Immunoglobulin A

IgG = Immunoglobulin G

ELI = Enzyme-Linked Immunosorbent Assay

NEU = Neutralization Assay

CLIA = ChemiLuminescence ImmunoAssay

NA = Not applicable

mlU = milli International Units; U = Units; IU = International Units

ED 50 = Estimated dose 50%

ECL: ElectroChemiluminescence

³ The assay cut-off for Hib may be subject to change.

The GSK Biologicals' clinical laboratories have established a Quality System supported by procedures. The activities of GSK Biologicals' clinical laboratories are audited regularly for quality assessment by an internal (sponsor-dependent) but laboratory-independent Quality Department.

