5.7.4. Biological samples evaluation

5.7.4.1. Immunological read-outs

The priority rank and immunological read-outs are given in [Table 8](#).

Table 8 Immunological read-outs

Blood sampling time-point		No. subjects	Component	Components priority rank
Type of contact and time-point	Sampling time-point			
Visit 4 (Month 5)	Post-Vacc	All	PRP	1
			D	2
			T	3
			Poliovirus serotypes 1, 2 and 3	4
			HBs	5
			PT	6
			FHA	7
			PRN	8
			13 S pneumoniae serotypes	9
			HRV	10

PRP: polyribosyl-ribitol-phosphate, PT: pertussis toxoid, FHA: filamentous hemagglutinin, PRN: pertactin, HBs: hepatitis B surface antigen, D: diphtheria, T: tetanus, HRV: human rotavirus.

In case of insufficient blood sample volume to perform assays for all antibodies, the samples will be analyzed according to priority ranking provided in [Table 8](#).

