10.5. Derived and transformed data

- A seronegative subject is a subject whose antibody concentration is below the cut-off value.
- A seropositive subject is a subject whose antibody concentration is greater than or equal to the cut-off value. The applicable thresholds are presented in [Table 7](#).
- A seroprotected subject is a subject whose antibody concentration is greater than or equal to the level defining clinical protection. The following seroprotection thresholds are applicable:
 - anti-D antibody concentrations ≥ 0.1 IU/mL.
 - anti-T antibody concentrations ≥ 0.1 IU/mL.
 - anti-HBs antibody concentrations ≥ 10 mIU/mL.
 - anti-poliovirus types 1, 2 and 3 antibody titers ≥ 8 ED50.
 - anti-PRP antibody concentrations ≥ 0.15 μ g/mL.
- Other cut-offs to be considered:
 - anti RV IgA antibody concentration ≥ 90 U/mL.
 - anti-pneumococcal serotypes (1, 3, 4, 5, 6A, 6B, 7F, 9V, 14, 18C, 19A, 19F, 23F) antibody concentrations ≥ 0.35 μ g/mL for the ELISA.
 - anti-PRP antibody concentrations ≥ 1.0 μ g/mL.
- The GMC calculation will be performed by taking the anti-log of the mean of the log concentration transformations. Note that antibody concentrations below the cut-off of the assay will be given an arbitrary value of half the cut-off while antibody concentration above the assay cut-off but below the Limit of Quantification will be given the assay cut-off as value.

Handling of missing data:

Immunogenicity:

- For a given subject and a given immunogenicity measurement, missing or non-evaluable measurements will not be replaced.

Reactogenicity and Safety:

- For analysis of solicited, unsolicited AEs (such as SAEs or AEs by primary MedDRA term), and for the analysis of concomitant medications, all vaccinated subjects will be considered. Subjects who did not report the event or the concomitant medication will be considered as subjects without the event or the concomitant medication respectively.

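### SAP 11.2.4 sets a result reported as below a value that exceeds the assay cut-off to that value, so undetermined and some known-negative results would count as meeting co-primary thresholds if they occur

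*SAP*

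**What the plan says.** In SAP 11.2.4 the "numerical immuno result is derived from a character field (rawres") by a list of rules. Three of them matter here:

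- `< value` at or below the cut-off: "value<=assay cut_off, numeric result =assay cut_off/2", so the infant is negative.
- `< value` above the cut-off: "value>assay cut_off, numeric result =value".
- `<= value` at or above the cut-off: also set to the value.

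The list is not limited to GMC calculation. Only formats that it does not cover are blanked ("else numeric result is left blank").

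Protocol 10.5 counts an infant as seroprotected when the concentration is at or above the threshold. For GMCs, it says that a result above the cut-off but "below the Limit of Quantification will be given the assay cut-off as value". The anti-HBs note in SAP 11.2.4 does the same for GMCs: results between 6.2 and 7.65 mIU/mL become 6.2.

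**The concern.** A result reported as below some value carries only an upper bound. Setting it to that bound gives the infant the highest concentration that the report allows. Where the bound is at or above the seroprotection threshold, the infant is scored as protected, although the report shows either that the status is unknown or that the infant is below the threshold.

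These numbers feed the co-primary seroprotection criteria. The laboratory is blinded (protocol 5.3), so the error should fall on both arms alike. In a superiority trial that would be conservative. In a non-inferiority trial, moving infants from failure to success in both arms shrinks a real deficit and works toward the desired conclusion. The SAP's statement that non-evaluable measurements are not replaced does not help, because the rule explicitly assigns these results a number.

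**Working it through.** **1. Inputs.** Cut-offs come from protocol Table 7, and thresholds from protocol 5.7.5 and 10.5. The reference rates, the margins and 416 evaluable infants per arm come from protocol Table 18. One-sided alpha is 2.5% (SAP 7.1). I use the Miettinen-Nurminen score method, which protocol 10.3.3 names for power, and assume that it also stands for the standardised asymptotic interval of the analysis.

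**2. The plan's own figures.** Table 18 gives type II errors of 4.8% (PRP ≥ 0.15), 4.4% (PRP ≥ 1.0) and 0.1% (IPV2). The normal approximation gives 4.77%, 4.37% and 0.02%. The two PRP figures agree; the IPV2 gap is immaterial. The stated errors sum to 0.1 + 4.8 + 4.4 + 3 × 0.1 = 9.6%, so the global power above 90% stands.

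**3. The rule applied to example results.**

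| Assay | Cut-off | Threshold | Reported | Set to | Scored | True status |
|---|---|---|---|---|---|---|
| Polio | 8 | 8 | `<8` | 4 | not protected | negative |
| Polio | 8 | 8 | `<16` | 16 | protected | undetermined |
| D or T | 0.1 | 0.1 | `<0.1` | 0.05 | not protected | negative |
| D or T | 0.1 | 0.1 | `<0.2` | 0.2 | protected | undetermined |
| PRP | 0.15 | 0.15 | `<0.15` | 0.075 | not protected | negative |
| PRP | 0.15 | 0.15 | `<0.3` | 0.3 | protected | undetermined |
| PRP | 0.15 | 1.0 | `<1.0` | 1.0 | meets threshold | known below |
| HBs | 6.2 | 10 | `<7.65` | 7.65 | not protected | negative |
| HBs | 6.2 | 10 | `<10` | 10 | protected | known below |

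For D, T, polio 1 to 3 and PRP ≥ 0.15 (six of the eight proportion criteria), every `< value` result above the cut-off passes. For HBs and PRP ≥ 1.0 it passes only if the value reaches 10 or 1.0.

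**4. Direction.** If a fraction f of the truly negative infants in each arm is scored as protected, a true difference Δ is observed as (1 − f)Δ. With Δ = −5% and f = 10%, that is 0.9 × (−5%) = −4.5%.

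**5. Size at the planned rates.** The documents give no frequency, so I ask how many misclassified infants would matter. Both arms are observed at the Table 18 rate, and k infants scored as protected, all in HRV Liq and all truly negative, are moved to failure. The lower limit is the d that solves (p₁ − p₂ − d)/SE(d) = 1.96, where SE(d) is the standard error under the restriction that the true difference is d.

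| Criterion | Successes per arm | k = 0 | k = 2 | k = 5 | First k that fails |
|---|---|---|---|---|---|
| PRP ≥ 0.15 (−5%) | 401 | −2.7% | −3.2% | −4.1% | 9 (2.2%) |
| IPV2 (−5%) | 411 | −1.7% | −2.4% | −3.3% | 11 (2.6%) |
| IPV1, IPV3 (−5%) | 414 | −1.3% | −2.0% | −3.0% | 12 (2.9%) |
| D, T (−10%) | 414 | −1.3% | −2.0% | −3.0% | 30 (7.2%) |

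With k = 10 moved in both arms, the limit goes only from −2.7% to −3.3% (PRP ≥ 0.15) and from −1.3% to −2.4% (IPV1, IPV3). No conclusion changes.

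**6. Size if the truth lies at the margin.** With HRV Lyo at the Table 18 rate and HRV Liq lower by exactly the margin, exact binomial summation gives this type I error for assumed values of f:

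| Criterion | f = 0 | f = 10% | f = 25% |
|---|---|---|---|
| PRP ≥ 0.15 | 2.4% | 4.7% | 12.4% |
| IPV1, IPV3 | 2.0% | 5.0% | 17.0% |
| D, T | 2.1% | 8.4% | 37.4% |

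For PRP ≥ 0.15, f = 10% means 416 × 0.035 × 0.10 = 1.5 infants in Lyo and 416 × 0.085 × 0.10 = 3.5 in Liq.

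**7. GMCs.** The generic list turns HBs `<7.65` into 7.65. Protocol 10.5 and the SAP's own HBs note give 6.2. A programmer cannot follow both. SAP section 9 does not list this as a change.

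**The case against.** The strongest reply is that the rule may never be used. SAP 11.2.4 describes the cut-off as the level below which nothing is quantifiable, so the usual negative is reported as below the cut-off and is scored correctly. Results such as `<16` or `<0.2` are illustrations, not results that the documents predict. This stands, and it limits the point to a rule that is wrong when triggered.

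A reader might infer that small-volume sera would produce such results by being tested at a higher starting dilution. The documents do not support this. For the situation described as "In case of insufficient blood sample volume to perform assays for all antibodies", protocol 5.7.4.1 runs assays by priority rank, and PRP, D, T and polio hold ranks 1 to 4.

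The Table 7 footnote ("The assay cut-off for Hib may be subject to change") also invites the inference that PRP `<0.15` would soon be scored as protected. That needs a lower cut-off with results still reported as `<0.15`, and nothing suggests this combination.

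Two neighbouring provisions do not add to the case. For `> value` results below the cut-off, "value<assay cut_off, numeric result =assay cut_off/2" scores possible positives as failures. That mainly adds failures and widens the interval, so it works against non-inferiority. The protocol 10.5 rule concerns GMCs, and a result set to a cut-off that equals the threshold would still pass. That conflict is therefore a GMC inconsistency, not evidence of inflated seroprotection.

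**Conclusion.** The point holds as a defect in the derivation rule with unknown and possibly zero effect. When triggered, the rule scores undetermined results as protected for six proportion criteria. For anti-HBs and anti-PRP ≥ 1.0 it can pass a result known to be below the threshold. Its direction, if such results occur in both arms, favours non-inferiority.

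The size rests on assumptions. At the planned rates, a few cases change nothing; reversing a 5%-margin criterion takes about 9 to 12 infants, all in HRV Liq and all truly negative. The type I error figures apply only if the true difference lies at the margin and the assumed share of negatives is misclassified.

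A reader might infer that even a small share of such results would hide most of the failures on a 5%-margin endpoint. That needs a frequency that the documents do not give, and nearly every such result would have to be truly negative. Nor is 1.8% the planned polio failure rate: it is an observed Table 16 figure (IPV2 at 98.2%), whereas Table 18 plans 0.5% (IPV1, IPV3) and 1.2% (IPV2).

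**What to change.** For the proportion endpoints, replace the `< value` and `<= value` rules with classification against each threshold T:

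- `< value` is below T if value ≤ T.
- `<= value` is below T if value < T.
- Otherwise the result is non-evaluable for T.

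Blanking results that are likely to be low can itself raise both rates. So add a sensitivity analysis that counts the non-evaluable results as not protected, and report their number by arm and assay. For GMCs, align the generic rule with protocol 10.5 and the HBs note.

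The cost is a few lines of SAP text and derivation code, settled before the final analysis, and possibly a few non-evaluable results per antigen. Those infants remain in the per-protocol set if another routine-vaccine antigen has a result, because protocol 10.4.2 requires only one.
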